7.3. Timing of Initiation and Duration of Treatment

After SCT the majority of acute GVHD occurs within the first 60 days. To ensure patients are stable prior to initiating maintenance therapy, the study will start no sooner than after the day 60 post-transplant bone marrow biopsy results are available. As many relapses occur within the first several months,⁹ subjects must be enrolled within 185 days of transplant or chemotherapy. Treatment with 5AC and GM-CSF must then begin within 14 days of enrollment. Approximately half of relapses occur within the first year after SCT, with 80% occurring within the first two years.⁹ Accordingly, we would limit the duration of maintenance therapy to one year and follow patients for an additional two years.

7.4. 5-Azacytidine (NSC 102816)

1. Chemical Name: 4-Amino-1-β-D-ribofuranosyl-1,3,5-triazin-2(1H)-one
2. Other Names: 5-Azacytidine, 5-AZA, Mylosar7, Ladakamycin, Vidaza
3. Supply: 5AC is supplied as 100 mg of white, lyophilized powder with 100 mg of mannitol, USP in 30 ml flint vials. The contents of each vial should be dissolved in 4mL of sterile water or 0.9% sodium chloride to provide a 25 mg/ml slurry. 5AC does not go into solution but forms loose slurry when reconstituted in this fashion. *Do not inject the slurry intravenously.* Single injections should not exceed 2ml. Doses requiring larger volumes may be split into multiple injection

sites if volume to be administered is too large. Injection sites should be rotated on a daily basis.

4. **Storage and Stability:** Store un-reconstituted vials at 25 degrees C (77 degrees F); excursions permitted to 15-30 degrees C (59-86 degrees F) (See USP Controlled Room Temperature). 5AC reconstituted for subcutaneous administration may be stored for up to 1 hour at 25 degrees C (77 degrees F) or for up to 8 hours between 2-8 degrees C (36 and 46 degrees F). The constituted solutions hydrolyze at room temperature and should be used within 30 minutes for delivery of maximum potency.

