9.4. Early Stopping Guideline for Futility and Simulations for Each Cohort

The simulation studies demonstrate the power for a sample size of 25 in each cohort. The study will be monitored for futility with a primary endpoint of two-year RFS. If the study meets the accrual goal of 10 patients per year per arm, 20 patients would be accrued by the time the first patient enrolled on study reaches the two-year efficacy endpoint. We will therefore monitor the study based on one-year RFS, knowing that if the one-year RFS is convincingly less than our targeted RFS at two years, the study would not meet its efficacy

objective and the trial should be halted. The non-parametric Kaplan-Meier estimate will be used to estimate the RFS function at one year.

The sample size of 25 and the study design operating characteristics assume a 2.5 year accrual period with an additional follow-up of one year. The null two-year RFS is 40% in the myeloablative group, 34% in the non-myeloablative group and 20% in the non-transplant cohort. We have designed each arm to stop early only if the posterior probability is 70% or higher that one-year RFS is less than that arm's null two-year RFS. Simulations were carried out with exponential survival and staggered patient entry. We assumed on average 10 patients will enter each arm of the study per year. Initial interim analyses occurred after 10 patients enrolled and was repeated every 5th patient to the maximum of 25. The interim analysis estimates of one-year RFS are based on analyses with an underlying Dirichlet process prior. We approximate the posterior distribution, which is actually a mixture of Beta distributions, the mixture depending on the amount of censoring, with a single Beta distribution. The parameters of this posterior Beta distribution are based on the number of failures and the effective sample size at one year, combined with the parameters of the prior.

The following tables summarize the operating characteristics under various scenarios for the underlying exponential RFS, based on 1000 simulations. The uncertainty of the null two-year RFS estimates are characterized with three priors: beta(2,3) in the myeloablative group (Table 5) and beta(2,4) in the non-myeloablative group (Table 6) and beta(1,4) in the non-transplant group (Table 7). This implies that our prior guess at the two year RFS for these three cohorts are respectively 40, 34 and 20%.

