9.5. Early Stopping Rules for Safety

This study will monitor acute grade III/IV GVHD in the two transplant arms. If it becomes evident that the proportion of acute grade III/IV GVHD convincingly exceeds 10%, the study will be halted for a safety consultation. The stopping rule will be applied to both transplant arms and will hold enrollment if the posterior probability of toxicity more than

0.10 is 75% or higher. The prior for this monitoring rule is $\beta(1,9)$. This means that our prior guess at the proportion of acute grade III/IV GVHD is 10%, and there is 90% probability that this proportion is between 0.57% and 28.3%. The operating characteristics of the stopping rule are given in the Table 8 and are based on 5000 simulations:

Toxicity stopping rule:

- Serious AE in 2 out of 2 patients. $\Pr(\text{Risk} > 0.1 | \text{Data}) = 0.91$
- Serious AE in 2 out of 3 patients. $\Pr(\text{Risk} > 0.1 | \text{Data}) = 0.889$
- Serious AE in 2 out of 4 patients. $\Pr(\text{Risk} > 0.1 | \text{Data}) = 0.866$
- Serious AE in 2 out of 5 patients. $\Pr(\text{Risk} > 0.1 | \text{Data}) = 0.842$
- Serious AE in 2 out of 6 patients. $\Pr(\text{Risk} > 0.1 | \text{Data}) = 0.816$
- Serious AE in 2 out of 7 patients. $\Pr(\text{Risk} > 0.1 | \text{Data}) = 0.789$
- Serious AE in 2 out of 8 patients. $\Pr(\text{Risk} > 0.1 | \text{Data}) = 0.762$
- Serious AE in 3 out of 9 patients. $\Pr(\text{Risk} > 0.1 | \text{Data}) = 0.902$
- Serious AE in 3 out of 10 patients. $\Pr(\text{Risk} > 0.1 | \text{Data}) = 0.885$
- Serious AE in 3 out of 11 patients. $\Pr(\text{Risk} > 0.1 | \text{Data}) = 0.867$
- Serious AE in 3 out of 12 patients. $\Pr(\text{Risk} > 0.1 | \text{Data}) = 0.848$
- Serious AE in 3 out of 13 patients. $\Pr(\text{Risk} > 0.1 | \text{Data}) = 0.828$
- Serious AE in 3 out of 14 patients. $\Pr(\text{Risk} > 0.1 | \text{Data}) = 0.807$
- Serious AE in 3 out of 15 patients. $\Pr(\text{Risk} > 0.1 | \text{Data}) = 0.786$
- Serious AE in 3 out of 16 patients. $\Pr(\text{Risk} > 0.1 | \text{Data}) = 0.764$
- Serious AE in 4 out of 17 patients. $\Pr(\text{Risk} > 0.1 | \text{Data}) = 0.888$
- Serious AE in 4 out of 18 patients. $\Pr(\text{Risk} > 0.1 | \text{Data}) = 0.873$
- Serious AE in 4 out of 19 patients. $\Pr(\text{Risk} > 0.1 | \text{Data}) = 0.858$
- Serious AE in 4 out of 20 patients. $\Pr(\text{Risk} > 0.1 | \text{Data}) = 0.842$
- Serious AE in 4 out of 21 patients. $\Pr(\text{Risk} > 0.1 | \text{Data}) = 0.825$

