- Serious AE in 4 out of 22 patients. $\Pr(\text{Risk} > 0.1 | \text{Data}) = 0.807$
- Serious AE in 4 out of 23 patients. $\Pr(\text{Risk} > 0.1 | \text{Data}) = 0.789$
- Serious AE in 4 out of 24 patients. $\Pr(\text{Risk} > 0.1 | \text{Data}) = 0.77$
- Serious AE in 4 out of 25 patients. $\Pr(\text{Risk} > 0.1 | \text{Data}) = 0.75$

Table 8

True Tolerability Risk	Prob. Declare Treatment Not Tolerable	Avg. Sample Size
0.02	1.5%	24.8
0.05	8.5%	23.7
0.10	34.8%	20.2
0.15	62.8%	16.0
0.20	81.8%	12.6
0.25	92.8%	9.7
0.30	97.8%	7.6

Operating characteristics of stopping rule based on 5000 simulations.

10. Data Safety and Monitoring Plan

The study PI will be responsible for the conduction of the study, including the monitoring of the study’s safety and oversight of the data collection. The PI will follow the Data Safety and Monitoring plan outlined in the Sidney Kimmel Comprehensive Cancer Center’s policy. This trial is designated as a category 1 protocol based on the risk and monitoring needs.

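### The GVHD stopping rule in section 9.5 does not define its denominator or observation window, and Table 8 assumes each outcome is known before the next patient enters, so it understates enrolment at a halt

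*Combined protocol and SAP*

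**What the plan says.** Section 9.5 names the event: "This study will monitor acute grade III/IV GVHD in the two transplant arms". Accrual to the transplant arms is held on the posterior probability that this risk exceeds a threshold; the threshold and limit are given as "0.10 is 75% or higher". The prior is beta(1,9). The boundary is a list of counts from 2 to 25 patients, including "Serious AE in 2 out of 8 patients" (posterior 0.762) and "Serious AE in 3 out of 9 patients" (0.902). The list labels the event a serious AE although the text monitors GVHD. Table 8 carries the note "Operating characteristics of stopping rule based on 5000 simulations" and says nothing about entry times or time to GVHD.

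Other sections bear on timing but do not close the gap:

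- Section 7.3: "Treatment with 5AC and GM-CSF must then begin within 14 days of enrollment".
- Section 5.3: 12 planned cycles, with 28 to 56 days between cycle starts.
- Section 10.2: adverse events are collected from first dose to 30 days after the last dose. This is a general collection period. It does not say when a patient counts as GVHD-free for the rule.
- Section 9.4, for the futility rule: "We assumed on average 10 patients will enter each arm of the study per year". That rule was simulated with staggered entry and uses an effective sample size to allow for censoring. Section 9.5 describes neither.

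**The concern.** The posterior treats each of the n patients as a completed yes-or-no outcome. At 10 entries per arm per year, with treatment running at least 12 × 28 = 336 days, many patients will be only part-way through their time at risk whenever the rule is checked. If they count in full, unobserved time is scored as freedom from GVHD and the rule acts late. If only completed patients count, the rule behaves differently again. Two competent readers could reach opposite decisions on the same data.

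This is the plan's only numerical safety boundary, and under sections 10 and 10.1 the study PI monitors safety, with committee review once a year. Table 8 is what tells reviewers how many patients would be enrolled before a halt if GVHD were excessive.

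**Working it through.** **1. Boundary.** With x events in n patients the posterior is Beta(1 + x, 9 + n − x), and the rule halts when Pr(risk > 0.10) ≥ 0.75. All 24 listed probabilities reproduce to rounding. The required count is 2 for n = 2–8, 3 for n = 9–16 and 4 for n = 17–25. Adding one event-free patient matters at two steps only:

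| Data | Posterior | Halt? |
|---|---|---|
| 2/8 | 0.762 | yes |
| 2/9 | 0.734 | no |
| 3/16 | 0.764 | yes |
| 3/17 | 0.741 | no |

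**2. Table 8.** An exact patient-by-patient binomial recursion over these boundaries, with each outcome known before the next entry, gives (halt probability / mean n):

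| True risk | Recomputed | Table 8 |
|---|---|---|
| 0.10 | 34.1% / 20.2 | 34.8% / 20.2 |
| 0.20 | 82.1% / 12.5 | 81.8% / 12.6 |
| 0.30 | 97.6% / 7.7 | 97.8% / 7.6 |

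The other four rows agree equally well. Table 8 is therefore an immediate-outcome calculation.

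**3. Staggered entry.** From the plan: 10 entries per year in one arm, maximum 25, boundaries as listed. Assumed: Poisson accrual, first dose 7 days after enrolment (the plan allows up to 14), GVHD onset uniform over a window from first dose, n = patients enrolled, and a check at each event. Between events n can only grow, so the posterior can cross only at an event. The plan gives no window, so a range is shown. Mean number enrolled at halt (25 if no halt):

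| True risk | Table 8 | 28 days | 3 months | 6 months | 12 months |
|---|---|---|---|---|---|
| 0.20 | 12.6 | 13.3 | 14.3 | 16 | 18.5 |
| 0.30 | 7.6 | 8.3 | 9.4 | 11.1 | 14.3 |

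The excess at 20% is 0.7, 1.7, 3.4 and 5.9 patients. At 30% it is 0.7, 1.8, 3.5 and 6.7.

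**4. Halt probability at 20% risk.** The chance of ever crossing is 81.2%, 80.8%, 79.8% and 78.0% for the four windows, against 81.8% in Table 8. The chance of crossing before the 25th patient enters, while there is still enrolment to hold, is about 77%, 75%, 70% and 61%. The immediate-outcome figure comparable with this second set excludes a crossing at patient 25 and is 80.2%.

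**5. How much the reading of n matters.** Suppose n counts only patients with an event or a completed window. Mean enrolment at 20% risk is then 12.9, 13.3, 13.8 and 15.2. At a true 10% risk the halt probability is 34.9%, 36.4%, 39.6% and 44.8%, against 32.3%, 31.6%, 29.2% and 27.0% when n counts enrolled patients. With a 12-month window, the undefined n alone moves the halt probability at the 10% reference risk from 27% to 45%.

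**The case against.** A reader might infer several stronger points. The documents do not support them.

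- *Enrolling another patient undoes a halt.* It does not. Section 9.5 holds enrolment once the limit is met, so after 2/8 no ninth patient enters. A ninth or seventeenth patient can only prevent a halt, by entering before the decisive event.
- *The undosed patient is the problem.* Numerically this is negligible. At 20% risk, enrolled and dosed denominators give mean enrolment of 14.4 and 14.4 (3 months) and 18.5 and 18.4 (12 months). The delay comes from time to event and partial follow-up.
- *The chance of detecting excess GVHD falls from 81.8% to about 61%.* That sets halting before accrual ends against ever halting. Like for like, the chance of ever halting stays at about 78 to 81%.
- *The rule counts enrolled patients.* The text says only patients. It neither states nor excludes enrolled, and since AE recording starts at first dose, counting patients with outcomes is a natural reading.

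The best argument on size is that the 12-month figures assume flat onset. Section 7.3 places most acute GVHD in the first 60 days after transplant, and treatment starts after that. If onset on study is early, the effect is small: an assumed exponential onset with mean 30 days gives 13.9 enrolled at 20% risk, about one patient more than Table 8. Sections 5.2.3 and 10.6 also hold therapy for an affected individual and allow the trial to be paused for unexpected serious toxicity.

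These arguments limit the size. They do not supply the missing window or denominator, or make Table 8 describe a trial with staggered entry.

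**Conclusion.** The concern holds as an incomplete rule with optimistic operating characteristics. Section 9.5 lacks an evaluability window and a definition of n, and Table 8 describes immediate outcomes. Under every delayed-onset scenario run, mean enrolment at halt for a true risk of 20% or 30% exceeds Table 8, even when only fully observed patients count.

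With n as enrolled patients, the understatement is about one patient if onset is short and about six to seven if it is spread over a year. Eventual detection is nearly unchanged. What is lost is timeliness, because more crossings come after the last patient has entered.

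The size rests on the assumed onset pattern, Poisson accrual at the planned rate and monitoring of each arm separately. Pooling the two transplant arms was not simulated. The 12-month column is the unfavourable end of the range, not an expectation. The point should be corrected. It does not invalidate the boundary, whose arithmetic is right.

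**What to change.** In section 9.5:

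1. State the GVHD observation window for this rule, counted from first dose. Its length is for the sponsor to set.
2. Count a patient in n from first dose, weighted by the fraction of the window completed, with weight 1 once an event occurs or the window ends. Evaluate Beta(1 + x, 9 + n − x) with this weighted n, keeping the prior and the 75% limit. This follows the effective-sample-size idea already used in section 9.4.
3. Evaluate at every acute grade III/IV GVHD event, and use that name in the boundary list.
4. Restate Table 8 under staggered entry at 10 patients per year, label the onset assumption, and report both the chance of ever crossing and the chance of crossing before accrual ends.

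The cost is a few sentences and one rerun simulation. With a 12-month window, weighting lowers mean enrolment from about 18.5 to 16.4 at 20% risk and from about 14.3 to 12.4 at 30%. At 20% risk it raises the chance of halting before accrual ends from about 60% to 72%. The price is a rise in halt probability at a true 10% risk from about 27% to about 34%, in line with the 34.8% the plan already accepts. Some delay is inherent: 16.4 is still 3.8 above Table 8's 12.6. Counting only completed patients is simpler and halts sooner, but events then enter before event-free patients do, which is why its halt probability at 10% risk reaches 44.8%.

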10.1. Data Reporting

This is a DSMP Level I High-Medium Risk study under the SKCCC Data Safety Monitoring Plan (9/22/2011). The Clinical Research Office QA Group will perform an audit after the first subject has been treated and then periodically depending on the rate of accrual and prior audit results. All trial monitoring and reporting will be reviewed annually by the SKCCC Safety Monitoring Committee. The PI is responsible for monitoring the study. Data must be reviewed to assure the validity of data, as well as, the safety of the subjects. The PI will also monitor the progress of the trial, review safety reports, and clinical trial efficacy endpoints and to confirm that the safety outcomes favor continuation of the study. The PI will be responsible for maintaining the clinical protocol, reporting adverse events, assuring that consent is obtained and documented, reporting of unexpected outcomes, and reporting the status of the trial in the continuing renewal report submitted to the IRB and to the trial monitoring review group. Content of the continuing renewal report at a minimum should include year-to-date and full trial data on: accrual and eligibility, protocol compliance, treatment administration, toxicity and ADR reports, response, survival, regulatory compliance, compliance with prearranged statistical goals. The report should be submitted in a timely manner according to the schedule defined by Johns Hopkins Medicine Institutional Review Board."

10.2. Adverse Event Definition

An adverse event (AE) is defined as any untoward medical occurrence in a patient or clinical investigation subject administered a pharmaceutical product, regardless of whether the occurrence is considered to have a causal relationship with treatment. An AE can therefore

be any unfavorable and unintended sign (including an abnormal laboratory finding), symptom, or disease temporally associated with the use of a medicinal (investigational) product, whether or not considered related to the medicinal (investigational) product. AEs are to be coded using an internationally recognized dictionary.

AEs will be recorded and reported beginning with the first dose of study drug. All events occurring between informed consent and the first dose will be recorded as medical history.

This study will utilize the Common Toxicity Criteria (CTC) version 4.0 for toxicity where applicable for adverse event reporting. In cases where CTC cannot be applied to the toxic event, the investigator will quantify the toxicity based on intensity as defined:

1. Mild: The subject is aware of signs or symptoms but they are easily tolerated; usually does not require additional therapy or discontinuation of study drugs.
2. Moderate: The signs and symptoms are sufficient to restrict but do not prevent usual activity; possible requires additional therapy but usually does not require discontinuation of study drugs.
3. Severe: The Subject is unable to perform usual activities and usually requires discontinuation of study drugs.
4. Life-threatening consequences; urgent intervention indicated.

Patients are to be followed for adverse events for 30 days after the last does of study drug and any adverse event occurring in a patient up to 30 days after stopping the study drug must be reported. The surveillance period after study drug discontinuation may be extended if there is a strong suspicion that the drug has not yet been eliminated or if the nature of a particular event may suggest long-term effects by the investigational drug, as assessed by the investigator.

10.3. Drug Relationship

The investigator will classify the study product relationship of an adverse event to the investigational product according to the following definitions:

1. None: The time course between the administration of study product and the occurrence or worsening of the adverse event rules out a causal relationship and or another cause is confirmed and no indication of involvement of the study product in the occurrence/worsening of the adverse event exists.
2. Unlikely: the time course between administration of the study product and occurrence or worsening of AE makes a causal relationship unlikely; the known effects of the study product or of the substance class provide no indication of involvement in AE and another cause adequately explains the AE; regarding the AE, a plausible causal chain may be deduced from the known effects of the study product or the substance class but another cause is much more probably; or another cause is confirmed and involvement of the study product in the AE is unlikely.

3. Possible: Regarding the AE, a plausible causal chain may be deduced from the pharmacological properties of the study product or the substance class, but another cause just as likely to be involved is also known; although the pharmacological properties of the study product or the substance class provide no indication of involvement in the AE, no other cause gives adequate explanation.
4. Probable: the pharmacological properties of the study product or of the substance class and/or the course of the AE suggest involvement of the study product in the AE, although another cause cannot be ruled out.
5. Definite: the pharmacological properties of the study product or of the substance class and the course of the AE indicate involvement of the study product in the AE and no indication of other causes exists.
6. Unclassifiable: only used for SAE: the available information is not sufficient for causality assessment.

10.4. Outcome

The investigator will record the outcome of the AE choosing one of the following categories:

1. Recovered/resolved
2. Recovering/resolving
3. Not recovered/ not resolved
4. Recovered/resolved with residual effects as specified
5. Fatal
6. Unknown

10.5. Serious Adverse Event (SAE) Definition

As defined by the FDA CFR 312, a serious adverse event is one, occurring at any dose (including overdose), that results in any of the following:

1. Death
2. Life-threatening illness
3. Inpatient hospitalization or prolongation of existing hospitalization
4. Persistent or significant disability or incapacity
5. A congenital anomaly or birth defect
6. An important medical event
7. Pregnancy

10.6. Adverse Drug Reaction and Toxicity Monitoring

The study team (research nurse, study coordinator or attending) will assign toxicity scores using the NCI common Toxicity Criteria version 4.03, weekly through the first cycle of therapy and at least every cycle thereafter. A copy of the CTC version 4.0 is available at the CTEP home page (<http://ctep.info.nih.gov>). If an unexpected and serious toxicity occurs that would result in patients being subjected to unacceptable risk, the trial will be placed on hold while this toxicity is investigated.

10.7. Toxicity Reporting

The Principal Investigator is responsible for the ongoing safety evaluation of the study. Unanticipated events will be reported to IRB as per JHMIRB policy 103.6b, *Organization Policy on reports of Unanticipated Problems Involving Risks to Participants or Others*. Expectedness of events will be determined by the product inserts for 5AC and GM-CSF. All other events will be logged on a Master AE Log as per SKCCC policy.

